11.5 IMMUNOLOGICAL TESTS

During the study, evidence of immune response to RST-001 will be monitored by systemic measurement of humoral and cellular immunity as follows:

[REDACTED]

These tests will be performed at several timepoints during the study: [REDACTED]

Immune responses will be measured qualitatively along with [REDACTED] [REDACTED] Immunogenicity results will be reported as positive or negative. The number and percent of patients with total negatives including patients with negative neutralizing antibody results as well as with negative binding antibody results will be tabulated at each visit by treatment group separately for each phase. A cumulative analysis that enumerate the number and percent of patients with positive antibody findings at any visit will be performed. Titer data will be summarized by means, standard deviations, minimum, and maximum.

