**General Exclusion Criteria:**

1. Participation in any investigational drug or device study within six months prior to Day 0;
2. Complicating systemic diseases or clinically significant abnormal baseline laboratory values. Complicating systemic diseases include those in which the disease itself, or the treatment for the disease, can alter ocular function. Examples are malignancies whose treatment could affect central nervous system function (i.e., radiation treatment of the orbit; leukemia with CNS/optic nerve involvement). For the procedure on establishing clinically significant abnormal baseline laboratory values, see Section [5.1.2](#).

3. Immunocompromising diseases, such as hepatitis B, C and HIV, or use of immunosuppressive medications
4. Females who are pregnant, nursing, planning a pregnancy during the study or who are of childbearing potential not using a reliable method of contraception during their participation in the study
5. History or current evidence of hypersensitivity to any component of the study treatment, medications, or diagnostic agents used in the study
6. Immunogenicity assays show presence of neutralizing antibodies to AAV2 above 1:1000 of dilution
7. Use of anti-platelets and anti-coagulants that may alter clotting within 28 days prior to study treatment administration
8. Any other condition that would not allow the potential patient to complete follow-up examinations during the course of the study and, in the opinion of the investigator, makes the prospective patient unsuitable for the study

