Ophthalmic and Medical History	X	X	X								
Concomitant medications and procedures	X	X	X	X	X	X	X	X	X	X	X
Adverse Events review	X	X	X	X	X	X	X	X	X	X	X
Physical Examination	X										
Pregnancy Test	X	X									
Blood Sample d	X	X									
Electrocardiogram (ECG)	X										
Chest X-ray	X										
Visual acuity	X										
Full Field Sensitivity Testing (FFST)	X	X									
Object detection and discrimination	X	X									
Pupillometry (at selected sites)			X								
Ambulation			X								
Complete Ophthalmic Examination	X	X									
Intraocular Pressure (IOP)	X	X									
Spectral Domain Optical Coherence Tomography (SD-OCT)	X	X									
Color Fundus Photography and Autofluorescence			X								
Electroretinography (ERG)	X										
Visual Evoked Potentials (VEP)			X								
Quality-of-life questionnaire			X								
Study drug administration f											

a Assessment administration may extend over more than one day.b If convenient, the Screening and Baseline visits may be combined.c Month 24 or early termination visit.d Blood samples will include hematology, chemistry and RST-001 immunogenicity testing; see [Appendix 2](#) for details.e IOP measurements will be performed pre- and post-injection in the study eye only. After the intravitreal injection, the patient will remain in the supine position and (IOP) intraocular pressure will be monitored for at least 30 min. In the event that the IOP is 30 mmHg or above, this will be managed according to Section [5.3.2](#).f Topical corticosteroid treatment may be given to the injected eye according to the investigator's standard of care.

**Table 3** Study Visit Schedule: Long-term Follow-up Visits

	Months		
	Clinic Visits		
Visit Windows (Month $\pm$ Days)	36 $\pm$ 30	48 $\pm$ 30	60 $\pm$ 30
Concomitant medications and procedures	X	X	X
Adverse Events review	X	X	X
Visual Acuity	X	X	X
Complete Ophthalmic Examination	X	X	X

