**Serology**

Human Immunodeficiency Viral Antibody  
Hepatitis B and C Antibody  
AAV2 antibody

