11.6 CLINICAL LABORATORY PARAMETERS

Descriptive statistics for clinical laboratory values (in SI units) and changes from the baseline values at each visit will be presented by treatment group separately for each phase for the following laboratory parameters as specified in the protocol amendment 2 (Section 20.2). Only patients with clinical laboratory data at baseline and at least one Post-treatment visit will be included in the summary.

CBC: complete blood count includes hemoglobin, hematocrit, red blood cell count, Mean Corpuscular Volume (MCV), Mean Corpuscular Hemoglobin (MCH), Mean Corpuscular Hemoglobin Concentration (MCHC), White blood cell count with differential, (neutrophils, lymphocytes, monocytes, eosinophils, basophils), and Platelet count.

Chemistry panel includes Sodium, Potassium, Blood Urea Nitrogen (BUN), Creatinine, Glucose, Chloride,

Liver function test include Albumin, Bilirubin, Total protein, Calcium, Alkaline, Phosphatase, AST (SGOT), ALT (SGPT), and Triglycerides.

Pregnancy test results from screening, baseline, and Month 24 will be listed.

Similarly, serology test results from screening visit only will be listed.

Clinical laboratory test values will be considered potentially clinically significant (PCS) if they meet either the lower-limit or higher-limit PCS criteria listed in [Error! Reference source not found.](#) The number and percentage of patients who have PCS Post-treatment clinical laboratory values will be tabulated by treatment group separately for each phase. The percentages will be calculated relative to the number of patients with available non-PCS baseline values and at least 1 Post-treatment assessment. The numerator will be the total number of patients with available non-PCS baseline values and at least 1 PCS Post-treatment value. A supportive tabular display of patients with PCS Post-treatment values will be provided, including the participant ID number, baseline and all Post-treatment (including non-PCS) values.

Table 11.6-1. Criteria for Potentially Clinically Significant Laboratory Results

Laboratory Parameter	SI Unit	Conversion Factor^a	Conventional Unit	PCS Criterion^b Low Value	PCS Criterion^b High Value
Hematology					
Hemoglobin	g/L	0.1	g/dL	< 0.9 × LLN	—
Hematocrit	Volume fraction	100	%	< 0.9 × LLN	—
Eosinophils	%	1	%	—	> 10
Neutrophils	%	1	%	< 30	> 90
Basophils	%	1	%	—	> 6
Monocytes	%	1	%	—	> 20
Lymphocytes	%	1	%	< 10	> 60
Absolute neutrophil count	× 10 ⁹ /L	1	1000/µL	< 1.0	—

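### The visible immunogenicity summaries in SAP 11.5 are not related to baseline, so the tables cannot separate antibody present at entry from antibody induced or boosted by RST-001

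*SAP*

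**What the plan says.** SAP 11.5 sets out to monitor for evidence of an immune response to RST-001. Its visible text gives the following outputs:

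- A binary result: "Immunogenicity results will be reported as positive or negative".
- A count and percentage of patients negative on neutralising and binding antibody, which "will be tabulated at each visit by treatment group separately for each phase".
- A cumulative summary: "A cumulative analysis that enumerate the number and percent of patients with positive antibody findings at any visit will be performed". Dose group is not mentioned here, and the text does not say whether the pre-dose visit is included.
- A titre summary: "Titer data will be summarized by means, standard deviations, minimum, and maximum". No scale, visit structure or change from baseline is stated.

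On entry status, Protocol 3.15.3.2 excludes a patient when "Immunogenicity assays show presence of neutralizing antibodies to AAV2 above 1:1000 of dilution". Antibody at or below that level does not exclude. Protocol Table 2 schedules blood at Screening and Baseline, and its footnote d says "Blood samples will include hematology, chemistry and RST-001 immunogenicity testing". Protocol Appendix 2 lists "AAV2 antibody" under serology, and SAP 11.6 says that "serology test results from screening visit only will be listed".

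**The concern.** A table about the response to a vector has to distinguish three kinds of patient: those who become positive after dosing, those who were positive and rose, and those who were positive and did not change. The visible outputs of 11.5 do not make that distinction, although entry-positive patients are allowed and the pre-dose sample exists.

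The SAP does make it elsewhere. In 11.1 a pre-existing adverse event becomes treatment-emergent only if it worsens. In 11.4 eye findings are counted by grade increase from baseline. In 11.6 patients already abnormal at baseline are left out of the rate of potentially clinically significant laboratory values. In 11.7 vital signs carry a change criterion. SAP 11.0 defines a pre-dose baseline for every safety parameter, but no visible summary in 11.5 uses it.

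The question matters in this trial. Protocol 3.11.1.2 names an immune response as a potential risk of RST-001. The dog study in Protocol 3.6.2.1 found dose-related ocular inflammation, with anterior uveitis in 8 of 8 high-dose eyes. Protocol 6.2.1 says that ocular immunogenicity has no diagnostic test. A reader will want to see, by dose, who developed antibody and who boosted.

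**Working it through.** The plan states no figure for this analysis, so there is none to reproduce. Enrolment is consistent: 3 + 3 + 3 + 12 = 21 at most, or 9 + 6 = 15 with the smaller Phase 2a.

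**1. What each table can show, by patient type**

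- *Negative before, positive after.* Counted as positive at any visit. Leaves the by-visit negative count, so the shift is visible there if the baseline visit is tabulated.
- *Positive before, positive after, titre unchanged.* Counted as positive at any visit, even if that means post-dose visits only. Never among the negatives.
- *Positive before, positive after, titre raised.* Counted exactly as the previous type in both tables.

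The cumulative count therefore merges all three types, and neither positive/negative table separates the last two. This follows from the binary scale and does not depend on any assumed rate.

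**2. How large the mixing could be**

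Let b be the share of patients positive at entry (assumed 0.2 to 0.6) and q the share of entry-negatives who convert (assumed 0 to 0.5). The documents give neither. Entry-positives are taken to stay positive.

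- Positive at any visit = b + (1 − b)q.
- Share of those already positive at entry = b / [b + (1 − b)q].

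With no treatment effect (q = 0):

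- 21 patients: 21 × 0.2 = 4.2 to 21 × 0.6 = 12.6 count as positive.
- 15 patients: 15 × 0.2 = 3 to 15 × 0.6 = 9.
- A treatment-emergent count would be 0.

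With conversion:

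- b = 0.4, q = 0.25: 0.4 + 0.6 × 0.25 = 0.55 positive, of whom 0.4 / 0.55 = 73% were positive at entry.
- Lowest share for q from 0.25 to 0.5: 0.2 / (0.2 + 0.8 × 0.5) = 33%.
- Highest share: 0.6 / (0.6 + 0.4 × 0.25) = 86%.

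The chance that a group of 3 holds at least one entry-positive patient is 1 − (1 − b)³, which is 49% at b = 0.2 and 94% at b = 0.6.

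**3. Titre means (all titres invented for illustration)**

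The fold rise is the geometric mean of each patient's post/pre ratio.

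- 20, 20, 640 going to 160, 160, 640: mean 226.7 to 320, ratio 1.41. Fold rise (8 × 8 × 1)^(1/3) = 4.0. Minimum and median both go from 20 to 160.
- 1000, 10, 10 going to 1000, 80, 80: mean 340 to 386.7, ratio 1.14. Fold rise 4.0. Minimum and median both go from 10 to 80.
- The same, but the high titre falls to 500: mean 340 to 220, ratio 0.65. Fold rise (0.5 × 8 × 8)^(1/3) = 3.17.
- Twelve patients, two stable at 1000 and ten going from 10 to 80: mean 175 to 233.3, ratio 1.33. Fold rise 8^(10/12) = 5.66.
- Counter-case, 100, 200, 400 going to 800, 1600, 3200: mean 233.3 to 1866.7, ratio 8.0. Fold rise 8.0.

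The mean understates the rise when a high stable or falling titre dominates it. It does not do so when all patients rise together.

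**The case against.** The case on the other side is substantial.

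- **The cumulative count is not the only summary.** Negatives are tabulated by visit, dose group and phase. If baseline is among those visits, net conversion of entry-negative patients is visible. This stands for induction. It does not help with boosting, because an entry-positive patient who stays positive is outside the negative count throughout.
- **The SAP does not call these findings responses.** A reader might infer that the plan reports prior exposure as response to RST-001. The text does not say so: it counts positive findings, and whether any visit includes the pre-dose visit is left open.
- **Boosts are not hidden.** A reader might infer that they are. In the first two titre examples the minimum moves 8-fold, and it is a planned statistic. SAP 15.1 adds median and quartiles for continuous variables, and 15.4 puts all assessments in the listings. With at most about 21 patients, individual profiles can be read. What remains is that no paired change is planned in the visible text, and classification from listings would be made after the data are seen.
- **The SAP does not say arithmetic.** That is the natural reading of an unqualified mean, but it is a reading.
- **Parts of 11.5 are blacked out**, including assays and time points, and table shells are in a separate document. The entry criterion concerns AAV2 neutralising antibody. It is plausible, but not shown, that the 11.5 tests use the same antigen and cut-off. The point therefore cannot be said to hold whatever the redacted text contains.

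**Conclusion.** The point holds in a limited form. On the visible text of SAP 11.5, the planned tables cannot separate antibody present at entry from antibody induced by RST-001 in the cumulative count, and cannot show a boost on the positive/negative scale. The titre summary may understate boosting in some configurations, and other planned outputs would partly correct that.

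The reasoning rests on two conditions: that some enrolled patients have antibody at or below the 1:1000 limit, and that the 11.5 assays detect it. The illustrative size (about 4 to 13 of 21 positive without any treatment effect, and 33% to 86% of positives already positive at entry when 25% to 50% of negatives convert) rests on assumed rates and contradicts no figure in the documents.

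This is a gap in descriptive safety reporting. It does not touch the sample size, the primary safety criterion (no related adverse event of grade 3 or greater) or the stopping rules in Protocol 7.4, none of which uses antibody status.

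**What to change.** Revise SAP 11.5 as follows:

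- Restrict the cumulative count to post-dose visits, and present it by dose group and baseline antibody status.
- Classify each patient as treatment-induced (negative before dosing, positive after), treatment-boosted (positive before, with a titre rise of at least a fold fixed in advance from assay variability), or neither.
- Summarise titres by geometric mean and geometric mean fold change from baseline, alongside individual profiles. State the value assigned to a titre below the lowest dilution, since a geometric mean needs one.
- State which assays these rules apply to, and whether they detect the AAV2 antibody used for eligibility.

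The cost is SAP wording and minor reprogramming. No new samples are needed, because pre-dose blood is already scheduled. SAP 4.0 and 16.0 still refer to Protocol Amendment 2, whereas the protocol now incorporates Amendment 4 and requires the analysis plan to be final before database lock (Protocol 11.3.6). The change can go into the same update.

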11.6 CLINICAL LABORATORY PARAMETERS

Descriptive statistics for clinical laboratory values (in SI units) and changes from the baseline values at each visit will be presented by treatment group separately for each phase for the following laboratory parameters as specified in the protocol amendment 2 (Section 20.2). Only patients with clinical laboratory data at baseline and at least one Post-treatment visit will be included in the summary.

CBC: complete blood count includes hemoglobin, hematocrit, red blood cell count, Mean Corpuscular Volume (MCV), Mean Corpuscular Hemoglobin (MCH), Mean Corpuscular Hemoglobin Concentration (MCHC), White blood cell count with differential, (neutrophils, lymphocytes, monocytes, eosinophils, basophils), and Platelet count.

Chemistry panel includes Sodium, Potassium, Blood Urea Nitrogen (BUN), Creatinine, Glucose, Chloride,

Liver function test include Albumin, Bilirubin, Total protein, Calcium, Alkaline, Phosphatase, AST (SGOT), ALT (SGPT), and Triglycerides.

Pregnancy test results from screening, baseline, and Month 24 will be listed.

Similarly, serology test results from screening visit only will be listed.

Clinical laboratory test values will be considered potentially clinically significant (PCS) if they meet either the lower-limit or higher-limit PCS criteria listed in [Error! Reference source not found.](#) The number and percentage of patients who have PCS Post-treatment clinical laboratory values will be tabulated by treatment group separately for each phase. The percentages will be calculated relative to the number of patients with available non-PCS baseline values and at least 1 Post-treatment assessment. The numerator will be the total number of patients with available non-PCS baseline values and at least 1 PCS Post-treatment value. A supportive tabular display of patients with PCS Post-treatment values will be provided, including the participant ID number, baseline and all Post-treatment (including non-PCS) values.

Table 11.6-1. Criteria for Potentially Clinically Significant Laboratory Results

Laboratory Parameter	SI Unit	Conversion Factor^a	Conventional Unit	PCS Criterion^b Low Value	PCS Criterion^b High Value
Hematology					
Hemoglobin	g/L	0.1	g/dL	< 0.9 × LLN	—
Hematocrit	Volume fraction	100	%	< 0.9 × LLN	—
Eosinophils	%	1	%	—	> 10
Neutrophils	%	1	%	< 30	> 90
Basophils	%	1	%	—	> 6
Monocytes	%	1	%	—	> 20
Lymphocytes	%	1	%	< 10	> 60
Absolute neutrophil count	× 10 ⁹ /L	1	1000/µL	< 1.0	—
Platelet count	× 10 ⁹ /L	1	1000/µL	≤ 75	≥ 700
White blood cell count	× 10 ⁹ /L	1	1000/µL	≤ 2.5	≥ 15
Chemistry					
Albumin	g/L	0.1	g/dL	< 0.9 × LLN	> 1.1 × ULN

Table 11.6-1. Criteria for Potentially Clinically Significant Laboratory Results

Laboratory Parameter	SI Unit	Conversion Factor^a	Conventional Unit	PCS Criterion^b Low Value	PCS Criterion^b High Value
Alkaline phosphatase	U/L	1	U/L	—	$\geq 3 \times \text{ULN}$
Alanine aminotransferase (ALT)	U/L	1	U/L	—	$\geq 3 \times \text{ULN}$
Aspartate aminotransferase (AST)	U/L	1	U/L	—	$\geq 3 \times \text{ULN}$
Gamma-glutamyl transferase (GGT)	U/L	1	U/L	—	$\geq 3 \times \text{ULN}$
Lactate dehydrogenase (LDH)	U/L	1	U/L	—	$\geq 3 \times \text{ULN}$
Blood urea nitrogen or Urea	mmol/L	2.8011	mg/dL	—	$> 1.2 \times \text{ULN}$
Calcium	mmol/L	4.008	mg/dL	$< 0.9 \times \text{LLN}$	$> 1.1 \times \text{ULN}$
Chloride	mmol/L	1	mg/dL	$< 0.9 \times \text{LLN}$	$> 1.1 \times \text{ULN}$
Total cholesterol	mmol/L	38.6698	mg/dL	—	$> 1.3 \times \text{ULN}$
High-density lipoprotein (HDL) cholesterol	mmol/L	39	mg/dL	$< 0.8 \times \text{LLN}$	—
Low-density lipoprotein (LDL) cholesterol	mmol/L	39	mg/dL	—	$> 1.2 \times \text{ULN}$
Creatine phosphokinase (CPK)	U/L	1	U/L	—	$> 1.5 \times \text{ULN}$
Creatinine	$\mu\text{mol/L}$	0.0113	mg/dL	—	$> 1.3 \times \text{ULN}$
Glucose, fasting	mmol/L	18.018	mg/dL	$< 0.8 \times \text{LLN}$	$> 1.2 \times \text{ULN}$
Magnesium	mmol/L	2	mEq/L	$< 0.9 \times \text{LLN}$	$> 1.1 \times \text{ULN}$
Potassium	mmol/L	1	mEq/L	$< 0.9 \times \text{LLN}$	$> 1.1 \times \text{ULN}$
Sodium	mmol/L	1	mEq/L	$< 0.9 \times \text{LLN}$	$> 1.1 \times \text{ULN}$
Total bilirubin	$\mu\text{mol/L}$	0.0585	mg/dL	—	$> 1.5 \times \text{ULN}$
Total protein	g/L	0.1	g/dL	$< 0.9 \times \text{LLN}$	$> 1.1 \times \text{ULN}$
Triglycerides, fasting	mmol/L	88.4956	mg/dL	—	$> 1.2 \times \text{ULN}$
Uric acid or Urate	$\mu\text{mol/L}$	0.0168	mg/dL	—	$> 1.1 \times \text{ULN}$

a Conversion factor from SI units to conventional (traditional) units.

b Criteria refer to SI units.

Blood urea nitrogen or Urea are the same parameters, and Uric acid or Urate are the same parameters.

LLN = lower limit of normal; PCS = potentially clinically significant; SI = *Le Système International d'Unités* (International System of Units); ULN = upper limit of normal laboratory reference range.

11.7 VITAL SIGNS

Descriptive statistics for vital signs (respiratory rate, temperature, systolic and diastolic blood pressures, and pulse rate) and changes from baseline values at each visit will be presented by treatment group separately for each phase.

Vital sign values will be considered PCS if they meet both the observed-value criteria and the change-from-baseline criteria listed in [Table 11.7–1](#). The number and percentage of patients with PCS Post-treatment values will be tabulated by treatment group separately for each phase. The percentages will be calculated relative to the number of patients with available non-PCS baseline values and at least 1 Post-treatment assessment. The numerator will be the total number of patients with available baseline values and at least 1 PCS Post-treatment value. A supportive tabular display of patients with PCS Post-treatment values will be provided, including the participant ID number, baseline and all Post-treatment (including non-PCS) values.

Table 11.7–1. Criteria for Potentially Clinically Significant Vital Signs

Parameter	Flag	Criteria^a	
		Observed Value	Change From Baseline
Sitting systolic blood pressure, mm Hg	High	≥ 180	Increase of ≥ 20
	Low	≤ 90	Decrease of ≥ 20
Sitting diastolic blood pressure, mm Hg	High	≥ 105	Increase of ≥ 15
	Low	≤ 50	Decrease of ≥ 15
Sitting pulse rate, bpm	High	≥ 120	Increase of ≥ 15
	Low	≤ 50	Decrease of ≥ 15
Weight, kg	High	—	Increase of ≥ 7%
	Low	—	Decrease of ≥ 7%

a A Post-treatment value is considered potentially clinically significant if it meets both the observed-value and the change-from-baseline criteria.

bpm = beats per minute.

11.8 ECG AND X-RAY

ECG and X-ray data will be collected only at screening. An interpretation of the ECG will be listed and summarized by treatment group separately for each phase. An interpretation of the x-ray will be listed.

11.9 OTHER SAFETY PARAMETERS

11.9.1 Physical Examination

The physical examination will be performed at screening visit, [REDACTED]. Physical examination findings from screening visit will be recorded on the Medical and Surgical History eCRF. Physical Examination findings at [REDACTED] or changes (worsening) since the previous physical examination, will be recorded on the Adverse Events eCRF. Summaries for medical/surgical history and adverse events are described in Sections 8.0 and 11.1, respectively.

12.0 INTERIM ANALYSIS

There will be three database locks. The primary analysis will occur when all patients have completed the Month 6 visit or exited earlier. The second analysis will occur when all patients have completed the Month 24 visit or exited early from the study. The final analysis will occur when all patients have completed the long-term follow-up or have been lost to follow-up.

13.0 DETERMINATION OF SAMPLE SIZE

The sample size for this study was chosen empirically; no formal sample size computations to meet power requirements were made. The sample size of approximately 3 patients for each dose group in Phase 1 are typical for dose escalation studies, an additional up to approximately 12 patients will be enrolled in Phase 2a for further safety and efficacy evaluation.

